### **8.3.4 Subgroup Analysis**

Subgroup analyses of the primary effectiveness and primary safety endpoints will be performed on the following subgroups.

- Gender
- Race/Ethnicity
- Procedure Type (e.g., TAVI, EVAR, etc.)

Time to Hemostasis will be analyzed by a one-way analysis of variance that includes the effect of the subgroup. If the subgroup means differ ( $p < 0.05$ ) then additional analyses will be performed to explore the cause of the difference, in particular if the differences are caused by another demographic factor.

Major Complications will be analyzed by Pearson's chi square to assess if the Major Complication rates differ between the levels of the subgroup. If the subgroup rates differ

( $p < 0.05$ ) then additional analyses will be performed to explore the cause of the difference, in particular if the differences are caused by another demographic factor.

### **8.3.5 Poolability Analysis**

Analyses of the primary effectiveness and primary safety endpoints will be performed to assess the comparability of study sites. Sites with fewer than 5 subjects each will be pooled into a composite site.

Time to Hemostasis will be analyzed by a one-way analysis of variance that includes the effect of the study site. If the study site means differ ( $p < 0.15$ ) then additional analyses will be performed to explore the cause of the difference, in particular if the differences are caused by differences in some baseline factor.

Major Complications will be analyzed by Pearson's chi square to assess if the Major Complication rates differ among study sites. If the study site rates differ ( $p < 0.15$ ) then additional analyses will be performed to explore the cause of the difference, in particular if the differences are caused by differences in some baseline factor.

### **8.3.6 Missing Data**

It is highly unlikely that there will be missing data for Time to Hemostasis, Technical Success, Ambulation Success, Time to Ambulation, Treatment Success or Procedure Time. However, if any of these endpoints are missing, the worst value observed for any subject at the same study site will be imputed for the missing value.

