## Results

The study population consisted of subjects who were candidates for non-emergent transcatheter interventional procedures via a 10-18F femoral sheath (e.g., TAVR, BAV, EVAR). Treated subjects were followed for 60 days post-procedure.

In total, 50 subjects were treated at 3 centers in Europe. The first subject was enrolled on 22 July 2015 and the last subject was enrolled on 27 January 2016. The first subject out was on 7 October 2015 and the last subject out was on 22 March 2016. Sixteen (16) subjects were treated with the 14F MANTA device (32%) and 34 were treated with the 18F MANTA device (68%). Of the enrolled subjects, 23 subjects were male (46%) and 27 were female (54%). Mean age was  $79.5 \pm 8.3$  years, mean weight was  $75.4 \pm 15.6$  kg, mean height was  $164.1 \pm 10.0$  cm, and mean Body Mass Index was  $27.8 \pm 4.4$  kg/m^2.

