### *Secondary Performance Endpoints*

The secondary performance endpoint Time to Hemostasis was to evaluate the elapsed time between MANTA deployment and the first observed and confirmed arterial hemostasis. Mean Time to Hemostasis was 2 minutes and 23 seconds (Standard deviation: 6 minutes and 38 seconds; Median: 24 seconds; Minimum: 2 seconds; Maximum: 37 minutes and 10 seconds). For 37 subjects (74%), Time to Hemostasis was reported as  $\leq 1$  minute; for 10 subjects (20%), 1 to 10 minutes were required until hemostasis was achieved; and for 3 subjects (6%), more than 10 minutes and manual pressure were required until hemostasis achievement

The secondary performance endpoint Time to Ambulation was to evaluate the elapsed time between MANTA deployment and when ambulation is achieved. Mean Time to Ambulation was 44 hours and 10 minutes (Standard deviation: 25 hours and 7 minutes; Median: 43 hours and 34

minutes; Minimum: 3 hours and 42 minutes; Maximum: 142 hours and 1 minute). For 5 subjects (10%), Time to Ambulation was reported as less than 24 hours; for 28 subjects (56%) Time to Ambulation was between 24 and 72 hours; and for 6 subjects (12%) more than 72 hours were required until ambulation. Hemostasis was maintained during ambulation for all subjects with available data (n=41).

The secondary performance endpoint Treatment Success was to evaluate the number of subjects that had Hemostasis Success and no Major Complications reported. Treatment Success was achieved in 47 subjects (94%). Absence of Hemostasis Success, as well as presence of one or more Major Complications, occurred in the same 3 subjects.

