5 DATA CONVENTIONS AND DEFINITIONS

5.1 Handling of Missing Data

Missing data will not be imputed for safety endpoints. However, if more than 13 subjects in the Primary Analysis Cohort either die for a reason other than a Major Complication or are lost to follow up within 30 days of treatment, then the rate of Major Complications will also be estimated by the Kaplan-Meier method, to allow for subjects who are censored before a Major Complication can be observed. See Section 2.4.1 for further details.

For effectiveness endpoints, it is highly unlikely that there will be missing data for Time to Hemostasis, Technical Success, Ambulation Success, Time to Ambulation, Treatment Success or Procedure Time. However, if any of these data are missing (i.e., in the event that Time to Hemostasis cannot be evaluated because a surgical repair must be performed), the worst value observed for any subject at the same study site within each analysis cohort, will be imputed for the missing value. Missing data for a subject in the Primary Analysis Cohort will be imputed with the worst value observed for any Primary Analysis Cohort subject at the same study site, and missing data for a subject in the Roll-In Cohort will be imputed with the worst value observed for any roll-in subject at the same study site.

No other imputations will be carried out for missing data.

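### Missing Time to Ambulation is called highly unlikely, yet 18–22% was missing in the sponsor's EU study; at that rate the site-worst-value rule could raise the reported mean by about 15–40%

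*Protocol*

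**What the plan says.** Protocol 8.3.6 sets the expectation: "It is highly unlikely that there will be missing data for Time to Hemostasis, Technical Success, Ambulation Success, Time to Ambulation", and likewise for the two other effectiveness endpoints. If a value is missing all the same, "the worst value observed for any subject at the same study site will be imputed for the missing value". SAP 5.1 repeats both statements and narrows the donor pool to the cohort: "the worst value observed for any subject at the same study site within each analysis cohort, will be imputed for the missing value". It then rules out any other imputation.

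Mean Time to Ambulation is a named secondary effectiveness endpoint (Protocol 5, SAP 2.6.2). It is reported without a formal test (Protocol 8.1.1, SAP 6.2.2) and has no performance goal.

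The EU pre-market study is summarised in Protocol 1.4: "In total, 50 subjects were treated at 3 centers in Europe". On ambulation it reports:

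- Shortest band: "For 5 subjects (10%), Time to Ambulation was reported as less than 24 hours"
- Middle band: "for 28 subjects (56%) Time to Ambulation was between 24 and 72 hours"
- Longest band: "for 6 subjects (12%) more than 72 hours were required until ambulation"

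It adds: "Hemostasis was maintained during ambulation for all subjects with available data (n=41").

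**The concern.** The expectation of almost no missing data covers six endpoints in one sentence. The sponsor's own earlier study fits it for Time to Hemostasis but not for Time to Ambulation. If the EU gap recurred, a rule meant for a stray missing value would apply to about one subject in five, each receiving the longest time recorded at the site.

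The rule also suits this endpoint poorly in kind. A subject who dies before walking has no ambulation time to recover, yet neither document makes an exception, so that subject receives another patient's time. The value depends on how many subjects the site happened to treat. Protocol 8.4 sets no minimum per site and a ceiling of 50, and the maximum of 50 times is usually far longer than the maximum of 3. A site with no observed time gives the rule nothing to use.

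At stake is a readable estimate of how soon subjects walk. No success criterion depends on it.

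**Working it through.** **Inputs** (Protocol 1.4, EU study): 50 treated; time categories 5, 28 and 6; 41 with data on hemostasis during ambulation; mean 44 h 10 min = 44.17 h; SD 25 h 7 min = 25.12 h; maximum 142 h 1 min = 142.02 h; 4 deaths.

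**1. Reproduce the printed percentages.** 5/50 = 10%, 28/50 = 56% and 6/50 = 12%, as printed. A denominator of 39 would give 12.8%, 71.8% and 15.4%; a denominator of 41 would give 12.2%, 68.3% and 14.6%. So the denominator is 50, and the categories sum to 78%.

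**2. Missing fraction.** From the categories: 5 + 28 + 6 = 39, so 11/50 = 22% are missing. From the 41 with ambulation data: 9/50 = 18%. For contrast, Time to Hemostasis in the same study was complete: 37 + 10 + 3 = 50. Even if all 4 deaths came before walking, which the summary does not say, 9 − 4 = 5 to 11 − 4 = 7 gaps would remain unexplained.

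**3. Upper case: every gap takes the EU maximum.** Imputed mean = (1 − f) × observed mean + f × imputed value.

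- f = 18%: (41 × 44.17 + 9 × 142.02)/50 = 61.8 h, or +40%. Imputed values supply 9 × 142.02/(50 × 61.8) = 41% of the total.
- f = 22%: (39 × 44.17 + 11 × 142.02)/50 = 65.7 h, or +49%. Imputed values supply 48%.

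**4. The rule as written: the site maximum.** The documents give no site-level times, so site maxima were simulated. Times were drawn from normal (cut off below at 3.7 h), gamma and lognormal distributions with the EU mean and SD. Layouts were 25 sites of 10, 13 of 20 and 5 of 50, with values missing at random. Ranges run across distributions and layouts.

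| Missing | Mean under site-worst rule | Change from 44.17 h | Every gap at 142.02 h |
|---|---|---|---|
| 22% | 52.0–61.6 h | +17.8% to +39.5% | 65.7 h (+48.7%) |
| 18% | 50.8–58.8 h | +15.1% to +33.2% | 61.8 h (+39.9%) |
| 5% | 46.3–48.7 h | +4.7% to +10.3% | 49.1 h (+11.1%) |
| 2% | 45.1–46.0 h | +2.1% to +4.1% | 46.1 h (+4.4%) |

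At 18–22% missing, imputed values supply 28–44% of the simulated mean.

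**5. Dependence on site size.** With lognormal times and 22% missing, the same population gives a mean of 52.7 h with 25 sites of 10 and 61.6 h with 5 sites of 50. The difference comes from site layout alone.

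**6. The median.** In the EU data 5 + 28 = 33 of 50 subjects walked by 72 h and 5 of 50 before 24 h. If all 11 gaps count as the longest times, or as not having walked, the 25th and 26th ordered values still lie between 24 and 72 h. The median stays in that band.

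**The case against.** The strongest reply is that the EU rate may not carry over. The summary is an abbreviated excerpt that gives no reason for the gaps and does not reconcile 39 with 41. The 41 counts data on hemostasis during ambulation, not times, and the number behind the 44.17 h mean is not stated. The pivotal protocol also has safeguards. Protocol 7.7 makes walking 20 feet a minimum condition for discharge readiness and asks sites to record the time, and exclusion 15 keeps out patients who are not mobile. All of this stands, and it may well lower the rate. It does not cover death before walking or a walk whose time was not written down.

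A second reply is that Ambulation Success already captures subjects who never walk, and that SAP 6.2.2 already lists the median. Both help in part. The site-worst rule also covers Ambulation Success, so a non-walker coded as missing at a site where everyone else succeeded would be counted as a success. The listed median would be taken after imputation, although step 6 shows that it is robust.

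A third is that worst-value imputation is a recognised conservative convention, here for an untested endpoint. That is fair, and it limits the consequence. The convention is less dependable when the donor is a small site whose longest time may be ordinary.

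A reader might go further and infer that the rule would largely determine the reported mean. The figures do not support that: observed values supply more than half of the mean in every scenario examined, including the upper case.

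**Conclusion.** The concern holds in a limited form. For Time to Ambulation, the stated expectation of almost no missing data conflicts with 18–22% missing in the sponsor's own EU study. If that rate recurred, the site-worst rule could raise the reported mean by roughly 15–40%, or about 7 to 17 h on the EU mean, with a ceiling of about 49%. At 2–5% missing the effect is about 2–11%. Separately from the rate, the rule gives subjects who die or never walk a finite time that depends on site size.

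The sizes assume that the EU mean, SD and maximum carry over, that values are missing at random, that sites are equal in size, and that the EU mean rests on 39 or 41 subjects. The bias generally runs against the device. Neither primary endpoint, the sample size nor any success criterion is affected.

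**What to change.** In SAP 5.1 and 6.2.2, for Time to Ambulation only:

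- Report the number missing with reasons, separating death before walking, discharge without walking, and walked with no time recorded.
- Make the observed-case mean and median the main summary.
- Add a cumulative-incidence curve with its median. Death, or discharge, without ambulation counts as not having ambulated, that is, as a competing event. Discharge should not be treated as censoring: it is tied to walking, so such censoring would be informative.
- State how a subject known to have walked, but with no recorded time, enters the curve.
- Keep the site-worst-value mean as a sensitivity analysis.
- Remove Time to Ambulation from the sentence that calls missing data highly unlikely, in the SAP and in Protocol 8.3.6.

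The cost is wording and one extra table or curve. Discharge date and time (Protocol 7.7) and date of death (Protocol 9.5.1) are already collected.

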## **8.4. *Minimum and Maximum Subject Recruitment for Analysis***

Study enrollment will be competitive. There is no minimum number of subjects that can be enrolled per site. However, no single site will be permitted to enroll more than 20% of the Analysis Cohort enrollment (i.e., 50 treated subjects).

There is also no minimum or maximum number of subjects defined in order to be included in the statistical analysis.

## 9 Adverse Events

### 9.1. Definitions

Refer to Section 4 for the definitions of the following terms associated with adverse events:

- Adverse Event
- Adverse Device Effect
- Device Deficiency
- Serious Adverse Event
- Serious Adverse Device Effect
- Unanticipated Adverse Device Effect
- Unanticipated Serious Adverse Device Effect

### 9.2. Potential Adverse Events and Adverse Device Effects

Potential Adverse Events and Adverse Device Effects associated with any large bore intervention, including the use of the MANTA VCD, include but are not limited to:

- Arterial damage
- Arterio-venous fistula
- Bleeding complications
- Bradycardia
- Closure device failure (lack of hemostasis)
- Compartment syndrome
- Death related to the procedure
- Deep vein thrombosis
- Dissection
- Ecchymosis
- Embolization
- Hematoma
- Infection at the puncture site which may require antibiotics or extended hospitalization
- Late arterial bleeding
- Limb ischemia
- Nerve injury or neuropathy
- Perforation
- Pressure in groin/access site region
- Pseudoaneurysm
- Retroperitoneal bleed
- Stenosis
- Transfusion due to blood loss resulting from the femoral arteriotomy procedure, or vascular repair
- Thrombus formation
- Ultrasound guided compression
- Vascular occlusion or repair
- Vessel laceration or trauma
- Wound dehiscence

### **9.3. Relationship of Adverse Event to Device/Procedure**

Each reported AE will be assessed by the Investigator for its primary suspected relationship to the closure device or to the interventional procedure.

- MANTA Study AEs related to the interventional procedure (e.g., TAVI, EVAR procedure) or closure of a non-target access site are considered Procedure-Related AEs.
- MANTA Study AEs related to the MANTA closure device and/or its deployment (in total, the closure procedure) are considered Device-Related AEs.
- MANTA Study AEs that are related to neither the interventional procedure nor the MANTA device are considered NOT related to the device or procedure.

The causal relationship of an AE to the device or procedure will be classified as follows:

- Not Related: An AE which cannot be attributed to the study device or initial study procedure.
- Unknown Relationship: The relationship of the AE to the device or procedure cannot be determined.
- Possible: The clinical event occurs within a reasonable time sequence to study procedure/study device and there is some evidence to “possibly” suggest a causal relationship. However, the influence of other factors such as underlying disease, concomitant medications, or concurrent treatment may have contributed to the event.
- Probable: The temporal sequence between the device use or procedures and the event is such that the relationship is likely or subject’s condition or concomitant therapy could have caused the AE.
- Definite: The clinical event occurs in a plausible time relationship to study procedure/study device and cannot be explained by any concurrent disease or other devices, drugs or chemicals.

### **9.4. Severity of Adverse Events**

The following categories will be used to describe the severity of an AE:

- Mild: awareness of a sign or symptom that does not interfere with the subject’s usual activity or is transient, resolved without treatment and with no sequelae.
- Moderate: interferes with the subject’s usual activity and/or requires symptomatic treatment.
- Severe: symptom(s) causing severe discomfort and significant impact on the subject’s usual activity and requires treatment.

### **9.5. Reporting of Adverse Events**

#### **9.5.1 SAE and AE Reporting to Sponsor**

All SAEs, irrespective of potential causal relationship to the device, procedure or study, that occur from the point of attempted MANTA placement onwards will be reported to the Sponsor within 24 hours of the Investigator’s first knowledge of the event. Suspected SAEs also should be reported.

The Investigator will forward information, via the eCRF system, about an SAE promptly, even if the information is incomplete or it is obvious that more data will be needed to form any

conclusions. This information will be available to the sponsor and CRO in the database. Additional information regarding the SAE will be recorded on the follow-up AE form forwarded to the Sponsor.

All AEs should be reported on the eCRF as soon as practicably possible. AEs will be recorded by their final medical diagnosis and not by each separate symptom. All AEs categorized by the Investigator as associated with the target artery and/or the ipsilateral leg, and all contralateral access site and systemic AEs categorized by the Investigator as possibly, probably or definitely device-related, will be reviewed by the Clinical Events Committee for a final adjudication. The information for the event will include the date of onset and resolution, the action taken, the corrective treatment and how the subject recovered with or without sequelae. In case of death, the relationship of death to the investigational device and/or the study procedure will be well documented. The date on which subject expired, what attempts were made to treat the event that led to death, the performance and functioning of the device during the event will be noted.

### **9.5.2 SAE Reporting to IRB and FDA – US**

The Investigator is responsible for reporting SAEs, in the required timeframe, to his/her IRB as required by the IRB.

The Sponsor is responsible for reporting UADEs to the U.S FDA in accordance with the IDE regulations (21 CFR Part 812). The results of any UADE evaluation will be reported to FDA and all reviewing IRBs and participating investigators within 10 working days after receiving notice of the UADE, per 812.150(b)(1).

The Sponsor will notify device-related SAE information to all active study Investigators as it becomes available.

### **9.5.3 SAE Reporting to EC and CA – EU**

As the MANTA device is CE-marked, device-related AEs and SAEs will be recorded by the Sponsor as complaints, in accordance with the Sponsor's Quality System. Such complaints will be analyzed to determine if vigilance reporting is required and any required vigilance reports filed in accordance with EU medical device vigilance requirements. AEs and SAEs that are not device-related will be handled only within the clinical study database and will not be reported as complaints.

### **9.5.4 SAE Reporting to IRB and CA – Canada**

The Investigator is responsible for reporting SAEs, in the required timeframe, to his/her IRB as required by the IRB. The investigator is also responsible for notifying Health Canada of any events that meet the definition of an "incident" under the Canadian Medical Device Problem Reporting requirements.

The Sponsor is responsible for reporting device-related incidents to Health Canada in accordance with the Canadian Medical Device Problem Reporting requirements.

### **9.6. Device Deficiencies**

The Investigator will record any device deficiencies, as defined in Section 4, in the eCRF. A device deficiency has occurred if an investigational device used in the study procedure failed to meet its performance specifications whether due to mechanical failure, malfunction or defects. Device deficiencies also include use errors and inadequate labeling. This applies to:

- devices used in the subject; or
- devices in which the package was opened, but the device was not used on the subject; or
- devices with which at least one insertion attempt was made, but the device did not remain in the subject.

If the device deficiency was associated with an AE, the reporting provisions for AE, ADE, SAE, SADE, UADE and USADE as outlined in above apply. Any device deficiency that did not lead to an AE but could have led to a SADE, if suitable action had not been taken, if intervention had not been made, or if circumstances had been less fortunate, must be reported to the Sponsor within 24 hours of the event using the eCRF. Reporting will follow the guidelines above. All device deficiencies will be recorded on the eCRF. Device deficiencies which could not have led to a SADE must be reported to the Sponsor within 3 business days. All devices alleged to be deficient must be returned to the Sponsor within 5 business days.

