## **Discussion**

### *Safety*

The 3 Major Complications reported were the only safety events that were classified as potentially or definitely device-related SAEs. For 2 of these events the Sponsor concluded that these events were a result of minor manufacturing deficiencies. Necessary corrective action has been taken to improve the manufacturing process and limit the associated safety risk.

In total, 10 AEs described an access site related hematoma > 6 cm. The investigator who treated these subjects, confirmed that this concerned an ecchymosis in 5 cases (50%), which is sometimes difficult to distinguish from a hematoma. This information was accompanied by ultrasound data in 3 cases, where the hematoma at the artery was assessed as 0.96, 2.28 and 0.82 cm^2. The 5 remaining cases concerned true hematomas based on visual assessment and available ultrasound data and those were classified as Minor Complications. No other Minor Complications were reported during the course of the study.

The AE termed 'stenosis at the access site' has only been reported at site 01. The observed difference in frequency proportion may be due to an interest bias. The involvement of an independent interpreter, e.g. by use of a qualified core lab, would limit the interpretation bias in future studies.

A large number of unrelated AEs can be anticipated with a study population as included in this study, with a mean age of 79.5 years (Standard deviation: 8.3 years; Median 80.7 years; Minimum 42.6 years; Maximum 90.4 years) and who are undergoing a significant intervention. Additionally, physical exam at baseline revealed that 46 subjects (92%) were suffering from one or more comorbid conditions prior to MANTA treatment.

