2.8.2 Procedural and Discharge Data

The following data will be collected during the procedure and discharge and analysis will be performed on both the Safety Evaluation Set and the Per Protocol population. A separate analysis will also be performed for the Roll-in subjects.

1. Endovascular procedure type
2. Procedure sheath brand
3. Procedure sheath size (F)
4. Index device manufacturer/brand
5. Index device size (mm)
6. Effective puncture size (F)
7. MANTA size (14F or 18F)
8. Target artery (left or right)
9. Target artery diameter (mm)
10. Sheath to femoral artery ratio (SFAR)
11. Pre-deployment ACT (sec)
12. Use of adjunctive methods to obtain hemostasis
13. Use of adjunctive methods for treating oozing
14. Any thrombus observed on the MANTA components (Y/N)
15. Post-deployment angiogram results

- 16. Time to discharge post-MANTA deployment
- 17. Time to discharge post-ambulation
- 18. Mean ABI scores at baseline, pre-procedure, post-procedure, discharge, follow-up
- 19. Ultrasound findings post-procedure and at follow-up
- 20. Device deficiencies

Other procedure data will be reported in by-subject listings. Definitions for these data points are provided in Section 6.2.3.

2.8.3 *Exploratory Analyses*

Additional exploratory analyses will be performed as needed.

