4 ANALYSIS POPULATIONS

The Primary Analysis Cohort will include all enrolled study subjects in whom an attempt to use the device is made, excluding the first two roll-in subjects treated per each Investigator. Subjects who sign the consent form but are deemed ineligible for the study prior to any attempt to use the MANTA device will not be included in the Primary Analysis Cohort or the Roll-In Cohort. Use of the MANTA puncture locating dilator at the beginning of the large-bore intervention procedure is not considered an attempt to use the MANTA device. Placement of the MANTA sheath following confirmation of intra-procedure exclusions is the start of attempted device use, and the time this sheath is removed will define the starting time of efficacy assessments.

The Primary Analysis Cohort, the Per Protocol Set, and the Safety Evaluation Set as described below will be comprised of the subjects in the Primary Analysis Cohort. Subjects in the Roll-In Cohort will be summarized separately from subjects in the Primary Analysis Cohort.

The following populations will be defined for the statistical analysis of this clinical trial:

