4.3 Safety Evaluation Set

The Safety Evaluation Set (SES) will consist of all non-roll-in subjects in whom an attempt to use the MANTA device was made. (i.e., subjects who sign the consent form but are deemed ineligible for the study prior to any attempt to use the MANTA device will not be included in the safety analyses). Subjects who are excluded due to intra-procedural exclusions will be excluded from the safety analyses as long as the MANTA sheath has not been introduced; use of the MANTA puncture locator at the beginning of the procedure is not considered "attempted use" of the MANTA device. The Safety population will be used for the analysis of safety endpoints as well as procedural and discharge data.

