6 STATISTICAL ANALYSIS METHODS

6.1 Summarizing and Tabulating Collected Data

All data from this clinical trial will be provided in data listings by site, subject, and time point, as applicable.

Continuous and categorical variables will be summarized by descriptive statistics. Standard descriptive statistics for continuous variables will be the number of observations, mean, median, standard deviation, minimum and maximum. Standard descriptive statistics for categorical variables will be counts and percentages; percentages will be computed relative to the size of the reference population. 95% confidence intervals will also be provided where appropriate.

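### The device deficiency table misses a deficiency found before the MANTA sheath is placed when no replacement MANTA follows

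*Protocol*

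**What the plan says.** Protocol 9.6 casts the net widely. It covers devices used in the subject, "devices in which the package was opened, but the device was not used on the subject", and devices with at least one insertion attempt that were not left in place. It adds: "All device deficiencies will be recorded on the eCRF". Protocol 13.5 likewise asks for failures, malfunctions and defects to be entered on the eCRF.

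The SAP handles deficiencies as item 20 of the procedural and discharge data in section 2.8.2, where "analysis will be performed on both the Safety Evaluation Set and the Per Protocol population"; roll-in subjects get a separate analysis. Section 4.3 confirms the choice of set: "The Safety population will be used for the analysis of safety endpoints as well as procedural and discharge data".

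Both sets depend on attempted use. Section 4.3 states: "The Safety Evaluation Set (SES) will consist of all non-roll-in subjects in whom an attempt to use the MANTA device was made". The Per Protocol Set is a subset of the Primary Analysis Cohort (4.2), which carries the same condition (4.1). Section 4 fixes when an attempt begins: "Placement of the MANTA sheath following confirmation of intra-procedure exclusions is the start of attempted device use". It also says that use of the puncture locating dilator at the start of the procedure does not count as an attempt, and it keeps consented subjects found ineligible before any attempt out of the Roll-In Cohort as well.

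SAP 6.2.3 counts instances of deficiency, by type and by MANTA size. For percentages in general, SAP 6.1 says "percentages will be computed relative to the size of the reference population". SAP 2.8.1 includes device deficiencies among the by-subject listings. Protocol 6.5.5 says that a subject who withdraws, or is exited by the investigator, before implantation leaves no data behind except why he or she left.

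**The concern.** The protocol records deficiencies by device and includes devices that never reached the subject. The SAP tabulates them on sets of subjects in whom the MANTA sheath was placed. The two populations differ in one place: a package is opened, the device is found deficient, and no MANTA sheath is ever placed. That is a failure serious enough to stop the device from being tried, so its absence from the table is not neutral.

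Deficiencies by size are a relevant descriptive output in a study meant to support a PMA. The sponsor itself linked deficiencies to harm in the EU pre-market study, where there were three Major Complications: "For 2 of these events the Sponsor concluded that these events were a result of minor manufacturing deficiencies" (Protocol 1.4, Discussion). A table that omits one of the protocol's own categories under some conditions would be read as complete when it is not.

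**Working it through.** The SAP states no deficiency rate, so there is no figure to reproduce. The check is to run the possible cases through the stated definitions.

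| Case | MANTA sheath placed? | In Safety Evaluation Set? | Instance in the 6.2.3 table? |
|---|---|---|---|
| (a) Device opened, found deficient, site closed another way | No | No | No |
| (b) First device opened and deficient, second MANTA then used | Yes | Yes | Yes |
| (c) Sheath placed, device then fails or is removed | Yes | Yes | Yes |
| (d) Two deficiencies in one treated subject | Yes | Yes | Yes, as two instances |

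The table is for non-roll-in subjects. The Per Protocol Set cannot rescue case (a), because it lies inside the Primary Analysis Cohort. For roll-ins, SAP 4 also ties membership to attempted use, though it spells this out less fully.

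Only case (a) is lost. Three further steps bear on it.

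1. **Can it happen?** Protocol 1.6.1 lists the puncture locating dilator as a component of the MANTA device. SAP 4 allows for its use at the start of the procedure, before the intra-procedure exclusions are settled, and does not treat this as an attempt. If the dilator comes from the same package (my inference from 1.6.1), a package can be open well before sheath placement, including in a subject who later fails an intra-procedure exclusion and so is never enrolled under Protocol 6.5.5.

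2. **Which way does the error run?** Let *n* be the instances tabulated and *m* the case (a) instances. The table shows *n*, while Protocol 9.6 calls for *n* + *m*. The missing share is *m*/(*n* + *m*), which is zero or positive and never negative. The documents give neither *n* nor *m*.

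3. **Is there another route into the report?** The SAP 2.8.1 listing states no attempted-use limit, so a recorded case (a) deficiency could appear there. However, Protocol 6.5.5 read literally keeps only the exit reason for a subject exited before implantation, while 9.6 wants the deficiency on the eCRF. Under 6.5.5 there may be nothing to list.

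**The case against.** The strongest reply is that this is a descriptive table, tested against nothing, and that the information is not lost. A by-subject listing is planned, SAP 6.1 promises listings of all trial data, and Protocol 9.6 requires reporting to the sponsor and return of every device alleged to be deficient. Most deficiencies would also be tabulated: anything after sheath placement, including failure of the handle, toggle, collagen or lock, and any deficient device replaced by another MANTA. All of that is right and limits the point. It does not remove it, because a listing gives no summary by size and Protocol 6.5.5 weakens the listing in exactly the case at issue.

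A reader might infer more than the documents support:

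- **That deficiencies are counted once per subject.** They are not. SAP 6.2.3 counts instances, and the count-once rule is in SAP 6.3, on safety data. What is true is that no denominator of devices opened is defined for any percentage.
- **That the EU study gives a deficiency rate of 2/50 = 4% from which to project the loss.** The 2 is the number of Major Complications that the sponsor put down to manufacturing deficiencies. It is not a count of deficiencies, and the synopsis gives no such total. Both events occurred in treated subjects, so their equivalents here would be in the table. The EU experience shows why deficiencies matter, not how many would be missed.
- **That every failure before insertion drops out.** Case (b) shows otherwise.

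One limit remains. SAP Appendix A, the list of tables, listings and figures, is not in the text available for this review, so a population specific to the deficiency table could not be checked there.

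**Conclusion.** The point holds in a narrow form. Under the stated definitions, a deficiency found before MANTA sheath placement, with no replacement MANTA then placed, falls outside every set on which the deficiency table is built, although Protocol 9.6 requires it to be recorded. The count can only err downward. Its size cannot be estimated from the documents and may be zero. Protocol 6.5.5 and 9.6 conflict over whether such data are kept at all.

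No primary endpoint, hypothesis or sample size is touched. This is a cheap improvement to completeness. It rests on reading SAP 4 literally and on Appendix A not setting a different population for this table.

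**What to change.** - **SAP 2.8.2 item 20 and 6.2.3:** tabulate every deficiency recorded under Protocol 9.6 for any subject for whom a MANTA package was opened, whether or not a sheath was placed. Split by MANTA size and by the three 9.6 groups, with roll-ins shown separately. Package opening is a better criterion than enrolment, because enrolment requires passing the intra-procedure exclusions. Keep the Safety Evaluation Set table as a secondary view.
- **Denominator:** report counts. Add a rate per device opened only if opened status is captured. The accountability items in Protocol 13.5 cover product code, lot, receipt, dispensing by subject number, and return or destruction, but do not list it, so check this and the eCRF first.
- **Protocol 6.5.5:** reconcile with 9.6 by stating that deficiency data are kept for subjects exited before implantation. Without this, the wider table may have nothing to draw on.

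The cost is SAP wording, one extra table and one clarifying sentence in the protocol. The reported deficiency count may be higher.
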